Due to several COVID related factors, including challenges with scheduling and some hesitation participants may have wearing a mask in the MRI scanner, some individuals will not receive the MRI portion of this experiment. This will neither affect our total enrollment goals, nor compromise the scientific integrity of the study. Moreover, it will lower the risk associated with MRIs to these participants.

Interventions and Interactions

Participants and Procedure. A total of 138 non-treatment-seeking nicotine-dependent men and women, 18-75 years old will be recruited from the local community using flyers, as well as traditional and social media outlets (radio, television, Facebook, Craigslist, local newspapers). Following initial contact, and informed consent, participants will be scheduled for a screening visit at WFUHS (inclusion/exclusion criteria described above). Participants must be motivated to quit and willing to make a quit attempt with the use of TMS and educational booklets for smoking alone ("Forever Free - A Guide To Remaining Smoke Free" Tobacco Research and Intervention Program). {Note: In the interest of experimental rigor, in this study we wanted to directly evaluate the efficacy of these 2 TMS strategies of smoking cessation without the confound of pharmacologic manipulation. Therefore, participants that would prefer to use pharmacotherapy immediately after the quit date will be referred to the WFUHS Smoking Cessation Treatment program and will not be eligible to enroll. Following the 4 week follow up, interested participants will be referred to a WFUHS Smoking Cessation Treatment program wherein they will have the opportunity to receive additional pharmacotherapies for smoking cessation}. Eligible participants will work with the clinical research team to set a quit date (within 2 weeks of the screening visit). They will be encouraged to set "Monday" as their quit date given prior studies that have shown higher motivation to quit on Mondays (120). They will be introduced to the Forever Free booklets at the first TMS visit. One aspect of these educational booklets will be discussed with the participants on each TMS visit. Although this program has low to moderate efficacy on its own (especially in the first 7 days), it is unlikely that TMS alone will be sufficient for smoking cessation. Therefore, all participants will also be exposed to these booklets by the Tobacco Research and Intervention Program.

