Study Visit 1 (Behavior, MRI, TMS) will begin 1 week prior to the quit date. **Inclusion/Exclusion criteria:** To participate in the present study, participants must: 1) be 18-75 years of age, (2) smoke at least 10 cigarettes a day (on average; as measured by 1 month timeline follow-back (TLFB), (3) not have a history of or current psychiatric or neurologic disease, or traumatic brain injury (4) not be pregnant, , (5) not currently use psychoactive substances other than alcohol, nicotine, or marijuana; nor have current or recent (e.g. within the past 5 years) moderate/severe substance use disorder (DSM-V) (6) not have any barriers to making contact between the TMS coil and the skin (e.g. braids that cannot be removed), and 7) meet all criteria on a standardized MRI/TMS safety screen (TASS) (including but not limited to implanted electronic devices, bullets or metallic fragments, hair clips and piercings that cannot be removed). These inclusion/exclusion criteria are those used in Study 4 described in Preliminary Research. **Randomization.** Participants will be individually randomized and assigned to treatment or control conditions using stratified block randomization (with blocks of randomly varying sizes) prior to the study.

Experimental Procedure (Aim 1 and 2): Screening Visit – Consent. Participants will receive a series of assessments designed to evaluate nicotine dependence and use, psychiatric conditions, and mood. These include a standard clinical intake evaluation screen for research (used in other studies by the PI), MINI International Neuropsychiatric Interview (MINI 5 P) (88), Timeline Follow-Back (TLFB) (89), Beck Depression Inventory II (BDI) (90), State-Trait Anxiety Inventory (STAI) (91) and Profile of Mood States (POMS) (92). Data will be collected using REDCapTM, and entered directly into the online portal to ensure security and prevent data loss.

During COVID-19, study personnel will interact with participants via the Wake Forest Baptist Health (WFBH) institutional WebEx videoconference software as necessary. Participants will remotely sign and date the informed consent document.

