Study Visit Procedures: At all visits, individuals will provide a urine screen to detect recent use of drugs of abuse and pregnancy, a breath carbon monoxide (CO) sample to detect recent cigarette smoking, and a breath sample to test for recent alcohol use. During the consent visit, visits 1, 6, 10 and follow up visits samples will be collected to determine cotinine (nicotine metabolites) levels in the urine. Samples will be taken from the urine sample provided for the drugs of abuse screen, no additional samples will be required from the participant. At visits 1, 6, 10 and follow up visits (Assessment visits), participants will complete a battery of behavioral assessments following active TMS or sham (see Table 2). MRI scanning (at visits 1 and 10) will occur prior to TMS in order to isolate cumulative, rather than acute, effects of TMS. At all visits participants will be required to provide a CO reading at least 50% of their baseline CO measure to ensure they are at least 6 hours deprived from cigarettes. Cigarette deprivation will be use to increase craving and responding for cigarettes. Short term cigarette deprivation has known amplification effects on the brain response to smoking cues (93, 94). Moreover, we have extensive experience with successfully using this deprivation procedure (33, 41).

Table 2 1. Biochemical and self-report assessment of tobacco use and dependence						
Measure	Time (Min.)	Visits	Description			
Carbon monoxide (CO Level)	1	1-10, and follow-ups	Breath CO provides an accurate measure of recent exposure to CO , including from smoking combustible tobacco products (95). The CO measurement will be used to determine recency of smoking.			
Timeline Follow-Back (TLFB) interview	5	1, 6, 10, and follow-ups	This self-reported tobacco product use interview asks participants to retrospectively estimate the number of tobacco products they've used each day for the past 30 days or since the previous assessment, whichever is fewer (89).			
Fagerström (FTND)	3	1, 6, 10, and follow-ups	This 6-item questionnaire quickly assesses degree of cigarette dependence (96, 97). Test for Cigarette Dependence.			
2. Measures of t	tobacco pr	oduct value an	d sensitivity (**PRIMARY DEPENDENT MEASURES)			

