Functional MRI Smoking Cue Reactivity Task (acquired after behavioral assessments)	15	1, 10	This task has been used in 4 original research publications by our group and reliably activates orbitofrontal and medial prefrontal regions (7, 11- 13). We will give participants an unlit cigarette to hold in their hand while they are in the MRI scanner. They will receive two 12m runs of the task (fixed within subject, counterbalanced within groups). During one run they will be instructed to 'allow' themselves to crave (passive limbic engagement) and in the other run they will be told to 'resist' the cues (executive engagement). When the task begins participants are shown pseudorandomly interspersed blocks of images: 1) cigarette images (e.g., cigarettes, lighters, people smoking) (CIG), 2) neutral images,			

			chromatically matched to the CIG images (NEU), and 3) blurry non- images (BLUR). Stimuli are presented in six 120-s epochs, each consisting of four 24-s blocks of an image type (one block each of CIG, NEU, BLUR). Each block is followed by a 6-s washout period, allowing the hemodynamic response from the previous block to decline before the next is presented. Scanning parameters: Multislice gradient-echo echo planar imaging (TR=2200, TE=35 msec, field of view of 192 mm, voxel size 3.0 x 3.0 x 3.0 mm, 36 slices, 3 mm thickness, no skip).
2. Other Assessm	ents		
Confidence in Active or Sham TMS Assignment (Active vs Sham)	1	1, 6, 10	Participants will complete a form indicating their confidence (scale 1-10) in whether they are receiving active or sham treatment. Pooled accuracy from prior work in our collaborator's laboratory was 47.6% suggesting that individuals were not aware of the stimulation being received.
Minnesota Nicotine Withdrawal Scale (MNWS)	2	1 - 10 and follow-ups	Participants will be asked to rate a variety of mood and physiological symptoms associated with nicotine withdrawal (e.g., anxiety, attention, hunger). Total withdrawal scores will be measured using the 8-item MNWS originally adapted from Hughes and Hatsukami 1986 (102) and Hughes 1992 (103). The 8-item scale is a validated measure and the most frequently used (104, 105).
Beck Depression Inventory (BDI)	10	1,6,10,and follow-ups	Given that iTBS to the left dlPFC improves depression scores, we will perform a mediation analysis to determine if any effects observed on smoking behavior and the brain response to smoking cues is related to changes in depression

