After the MRI scanning visits participants will be escorted into the Brain Stimulation Research Laboratory ([name] research suite) where scalp localization will be performed for the TMS procedure. The Cartesian position of the coil (X,Y,Z) will be determined by standardized positions from the EEG 10-20 system: 1) AFZ will be used for the mPFC stimulation (Aim 1), 2) F3 will be used for the left dlPFC stimulation (Aim 2). The angular position of the coil (pitch, yaw, roll) will be determined by the individual's cortical geography using the individual's T1 scan for guidance. The locations and coil orientation will be indicated on a nylon cap which will be worn during the TMS sessions. We will then determine the participant's resting motor threshold (RMT, the minimal amount of stimulation required over the hand area of the primary motor cortex to induce contraction of the APB muscle of the hand 50% of the time) via the standardized PEST procedure (106, 107). The procedures for acquiring the motor threshold, performing cortical localization, standardized procedures, blinding, establishing standardized paradigms and training regimens for all staff, as well as safety and ring the experimental procedures are consistent with our prior publications (7,27, 54, 63, 69, 78, 111). We will also publish a Standard Operating Procedure document and video file as supplementary material with any publications that arise from this project (as in 111, supplement).

For Aim1 (Strategy 1) stimulation will be over mPFC. For Aim 2 (Strategy 2) stimulation will be over the left dlPFC. The Aims will be pursued in serial, with a 2:1 active versus sham randomization for each Aim. Participants will receive 20 trains of stimulation (1200 pulses total; each train: 3 pulse bursts presented at 5Hz, 15 pulses/sec for 2 sec, 8 sec rest, 10 pulses/train; 110% RMT, MagPro) using a figure 8 coil (Coil Cool-B65 A/P). This is the iTBS sequence initially published (3) which has been used in clinical depression treatment (46). During each real and sham TBS session each day the amplifier output will be escalated ("ramping" in 5% increments over 30 seconds) up to 80% to 110% RMT to enhance tolerability. The time between the end of the TBS procedures and the beginning of the behavioral assessments will be compiled and used as covariates in subsequent analyses.

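### The documents place the Visit 1 and Visit 10 behavioural battery both before and after TMS, and the primary behavioural analysis uses change from a baseline that is not defined.

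*Combined protocol and SAP*

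**What the plan says.** The Study Visit Procedures make two timing statements in succession. On the battery: "At visits 1, 6, 10 and follow up visits (Assessment visits), participants will complete a battery of behavioral assessments following active TMS or sham". On imaging: "MRI scanning (at visits 1 and 10) will occur prior to TMS in order to isolate cumulative, rather than acute, effects of TMS". The TMS Treatment section fits the first: "The time between the end of the TBS procedures and the beginning of the behavioral assessments will be compiled and used as covariates".

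Table 2 labels the imaging row "Functional MRI Smoking Cue Reactivity Task (acquired after behavioral assessments". The Participants and Procedure section introduces the first visit in the matching sequence: "Study Visit 1 (Behavior, MRI, TMS) will begin 1 week prior to the quit date".

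Table 2 schedules the purchase task and delay discounting at Visits 1, 6, 10 and follow-up, and the QSU at every treatment visit and follow-up. It also schedules an active/sham form at Visits 1, 6 and 10: "Participants will complete a form indicating their confidence (scale 1-10) in whether they are receiving active or sham treatment". The Design section adds weekly maintenance TMS during follow-up, with weekly behavioural assessments over the first four weeks.

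Outcome Measure(s), Behavioral Outcomes, specifies a repeated measures ANOVA of change from baseline with time (days 1, 6 and 10), group and their interaction, and makes the interaction the primary hypothesis. No section says which measurement is the baseline. The screening paragraph opens its list of assessments with "These include a standard clinical intake evaluation screen for research" and names no primary behavioural measure. The Power paragraph assumes four time points. The COVID paragraph after it says that "some individuals will not receive the MRI portion of this experiment".

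**The concern.** A site following the Study Visit Procedures takes the Visit 1 battery after the first real or sham session. A site following Table 2 takes it before. If Visit 1 is the baseline, the first practice gives a post-randomisation baseline that may already contain part of the treatment effect. All six primary behavioural outcomes are affected (demand Q0 and alpha, two QSU factors, discounting at two magnitudes), as are the baseline discounting and cigarette valuation moderators in the Design section. The neuroimaging outcome is not, since imaging is placed before TMS.

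Separately, the primary model cannot be run unambiguously as written, because day 1 appears to be both the reference and an outcome level. A pre-TMS value that was never collected cannot be recovered later.

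**Working it through.** **1. Order at Visits 1 and 10.** Write B for battery, M for MRI, T for TMS.

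- Table 2, imaging row: B before M.
- Study Visit Procedures, imaging sentence: M before T.
- Together: B before T.
- Study Visit Procedures, battery sentence: T before B. The TMS Treatment covariate presupposes the same.

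The two orders are incompatible for a single battery. The conflict does not need the parenthesis describing Visit 1, which may only list components. Visit 6 has no MRI, so only T before B applies there. The active/sham form can only follow the first session at Visit 1, but that does not fix the position of the primary measures.

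**2. Baseline.** If baseline is the Visit 1 value Y1, the day-1 change is Y1 − Y1 = 0 for everyone, with zero variance. For illustration, assume SD 1 and AR(1) correlation 0.5 between adjacent assessments:

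- Var(Y6 − Y1) = 2(1 − 0.5) = 1
- Var(Y10 − Y1) = 2(1 − 0.25) = 1.5
- Cov(Y6 − Y1, Y10 − Y1) = 0.5 − 0.5 − 0.25 + 1 = 0.75
- every day-1 entry = 0

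The matrix is singular and fits neither AR(1) nor compound symmetry with a common variance. The zero day-1 row arises whatever the correlation.

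**3. What each order measures.** Let Lk be the lasting real-minus-sham effect after k sessions and a the same-day transient effect, taken as equal at each visit. Visit 10 minus Visit 1 is then:

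| Position of battery | Contrast |
|---|---|
| After TMS at both visits | (L10 + a) − (L1 + a) = L10 − L1 |
| Before TMS at both visits | L9 − 0 = L9 |
| Before at Visit 1, after at Visit 10 | L10 + a |

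With both after TMS, the transient part cancels and the lasting first-session effect L1 is subtracted. That attenuates the contrast if L1 has the sign of the later effect, inflates it if opposite, and does nothing if L1 = 0. The before-minus-after difference is L9 − (L10 − L1) = L1 − (L10 − L9), which is zero if the first and last sessions add equally.

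If Visits 1 and 10 are before TMS and Visit 6 after, the changes are L6 + a at Visit 6 and L9 at Visit 10, so the transient effect enters only the middle time point.

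**4. Can a transient effect reach the battery?** The Innovation section gives up to an hour for a 600-pulse session; the TMS Treatment section specifies 1200 pulses and no duration. The Table 2 times, excluding imaging, are 1 + 5 + 3 + 2 + 5 + 5 + 1 + 2 + 10 + 10 = 44 minutes, of which the primary measures take 2 + 5 + 5 = 12. The whole battery fits within an hour only if it starts within 60 − 44 = 16 minutes of TMS. Overlap is possible, not certain.

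**5. Which test goes with which scores.** Let D6 and D10 be the real-minus-sham differences in change at Visits 6 and 10.

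- Raw scores at Visits 1, 6, 10: with no group difference at a pre-TMS Visit 1, the profile is (0, D6, D10), and the interaction detects any departure from zero.
- Change scores at Visits 6 and 10 only: the interaction tests D10 − D6. If D6 = D10, it tests nothing, however large the effect.

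For example, assume an equal effect s per session and assessment before TMS. Then D6 = 5s, D10 = 9s, and the interaction sees 4s, or 4/9 = 44% of the Visit 10 effect. Dropping day 1 while keeping the interaction as the primary test would therefore weaken the analysis.

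**The case against.** The strongest reply is that a post-TMS battery was intended. The battery sentence is explicit, the next sentence treats MRI differently and gives a reason, and a covariate is specified for the interval after stimulation. The opposing order rests partly on a parenthesis in a table row. This stands as far as Visits 6 and 10 go: testing after TMS there is a legitimate choice of what to estimate. It does not remove the contradiction with Table 2, and it makes the baseline question more pressing.

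A second reply is that an earlier baseline may exist. The screening list is open-ended, and four time points would fit one pre-treatment measurement plus three visits. That is possible, so one cannot say that no earlier measurement is taken. But none is scheduled, and Table 2 starts every primary behavioural measure at Visit 1.

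Third, the harm may be nil, and steps 3 and 4 allow that.

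A reader might infer more than the documents support:

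- **That the treatment effect will be diluted or the trial lose a stated amount of power.** No size for a first-session behavioural effect is given, and its sign is unknown.
- **That scanned and unscanned participants will be tested in different orders.** For those without MRI only the post-TMS statement applies, so this could happen, but no section prescribes it.

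**Conclusion.** The contradiction at Visits 1 and 10 follows from the text alone. The baseline for the primary behavioural change scores is undefined, and if it is Visit 1 the day-1 level carries no information. If the Study Visit Procedures are followed, that baseline and the baseline moderators are measured after treatment has begun.

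The direction and size of any resulting bias cannot be derived from the documents. It is zero if the first session does not affect the battery, or affects it only transiently and equally at each visit. The contrasts in step 3 assume one session per visit and additive lasting and transient effects; they show what each order measures, not how large the bias is. The correction matters because it touches every primary behavioural outcome and a missed pre-TMS measurement cannot be recreated.

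**What to change.** 1. Reconcile Participants and Procedure, Study Visit Procedures, Table 2 and TMS Treatment. At Visit 1, take the QSU, purchase task and discounting before the first TMS session for all participants, scanned or not, and define these values as the baseline. Leave the active/sham confidence form after TMS.
2. State one position relative to TMS for Visits 6 and 10, the follow-up visits with maintenance TMS, and the QSU at Visits 2–5 and 7–9, the same with and without MRI. Before TMS matches the imaging rationale and estimates the cumulative effect, with Visit 10 reflecting nine completed sessions. After TMS estimates cumulative plus acute effect and keeps the time-since-TBS covariate. Say which effect is estimated.
3. In Behavioral Outcomes, either analyse raw scores at Visits 1, 6 and 10 with group-by-time as the primary test, or analyse change scores at Visits 6 and 10 with the group effect, or a joint test of group and group-by-time, as primary. Do not use the interaction alone on Visit 6 and 10 change scores. Reconcile the choice with the four time points in the Power paragraph.
4. For participants already assessed, record the order used and flag it in the analysis.

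The cost is a small change in visit flow, with no new visit or instrument. A change part-way leaves two orders in the data, hence item 4.

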Questionnaire on Smoking Urges-Brief (QSU)	2	1 - 10 and follow-ups	This 10-item questionnaire assesses cigarette craving . Participants will be asked to rate from 1 (strongly disagree) to 100 (strongly agree) their agreement with several statements (e.g., "I have a desire for a cigarette right now," and "Nothing would be better than smoking a cigarette right now."). Factor analyses support two factors: one that reflects a strong desire and intention to smoke and one that reflects relief from negative affect associated with an urgent desire to smoke (45).			
Hypothetical Purchase Task (**Demand Alpha, Q0) (HPT Cigarettes)	5	1, 6, 10, and follow-ups	The hypothetical purchase task (HPT), a validated measure for cigarette demand, (98, 99) will assess cigarette purchases at various price conditions. Participants will hypothetically purchase quantities of cigarettes to use over a 24-hour period across ascending prices (e.g., \$0, 0.12, \$0.25, \$0.50, \$1.00, and \$2.00 per cigarette). The HPT has been shown to be predictive of treatment outcomes (100).			
3. Cognitive/beha	vioral tasl	k (** PRIMAR	Y DEPENDENT MEASURE)			
Delay- discounting tasks (*discounting rate, \$1K)	5	1, 6, 10, and follow-ups	Participants will be asked to choose between two conditions in which varying amounts and delays to behavioral outcomes (e.g., \$50 now or \$100 later) are presented. We will use magnitudes of \$100 and \$1000 which are the most thoroughly documented among the literature (101). Across consecutive choices, the delay to the larger outcome will be titrated until reaching the participant's indifference delay (i.e., the delay at which s/he equally values both options). This indifference delay indexes individual participants' rates of delay discounting. [61]. Monetary delay discounting has been documented to be predictive to treatment success for smokers (39).			
1. Brain Reactivity to Smoking Cues (**PRIMARY DEPENDENT MEASURE)						

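### The breath CO check is written as a minimum reading, which is the opposite of what is needed to show at least 6 hours without cigarettes

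*Combined protocol and SAP*

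**What the plan says.** The rule is in the protocol under Study Visit Procedures. At all visits, participants are "required to provide a CO reading at least 50% of their baseline CO measure to ensure they are at least 6 hours deprived from cigarettes".

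The surrounding text says what CO measures and why deprivation is wanted:

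- Every visit includes "a breath carbon monoxide (CO) sample to detect recent cigarette smoking".
- The carbon monoxide row of Table 2 says: "The CO measurement will be used to determine recency of smoking". Its visit column reads "1-10, and follow-ups".
- The reason for deprivation is given directly after the rule: "Cigarette deprivation will be use to increase craving and responding for cigarettes", and "Short term cigarette deprivation has known amplification effects on the brain response to smoking cues".

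The reading that serves as baseline is not named. The consent visit is named for a different assay: "During the consent visit, visits 1, 6, 10 and follow up visits samples will be collected to determine cotinine". The protocol does not state what happens when a reading fails the check.

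**The concern.** The wording is a minimum and the purpose requires a maximum. If CO marks recent smoking, deprivation lowers it, and a participant shows deprivation by reading low relative to baseline. A rule that demands at least half of baseline asks for the opposite.

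Two things are at stake. First, the check is meant to standardise the smoking state before the primary measures: craving, cigarette demand and delay discounting (Outcome Measures, Behavioral Outcomes), and cue reactivity (marked primary in Table 2). By the protocol's own account, deprivation raises craving and amplifies the brain response to cues, so a check that does not verify deprivation leaves that source of variation uncontrolled. Second, this is a quit-attempt trial. At visits after the quit date, the people whose CO has fallen furthest are those in whom early cessation has succeeded, and the literal rule fails them.

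**Working it through.** The question is the direction of an inequality, so there is no sample-size or power figure to reproduce.

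**Step 1: direction.** Inputs: the 50% threshold and the 6-hour purpose (Study Visit Procedures), and CO as a marker of recent smoking (same section and Table 2). Let r = CO reading / baseline CO.

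| r | Written rule (pass if r ≥ 0.50) | Rule matching the purpose (pass if r ≤ 0.50) |
|---|---|---|
| 1.20 | pass | fail |
| 1.00 | pass | fail |
| 0.75 | pass | fail |
| 0.50 | pass | pass |
| 0.40 | fail | pass |
| 0.25 | fail | pass |
| 0.10 | fail | pass |
| 0.00 | fail | pass |

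The rules agree only at r = 0.50. No elimination rate is needed for this result.

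**Step 2: visits affected.** The check applies at all visits. From Table 2, craving (the row beginning "This 10-item questionnaire assesses cigarette craving") is taken at all 10 treatment visits and at follow-ups. Demand and discounting are taken at 3 treatment visits (1, 6, 10) and at follow-ups. Cue-reactivity scans are taken at 2 (Visits 1 and 10). The primary behavioral ANOVA uses days 1, 6 and 10.

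**Step 3: Visit 10 against the quit date.** Take Visit 1 as day 0, with at most one session a day. The earliest Visit 10 is then day 9. The protocol dates the quit attempt in two ways:

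- One week after Visit 1 (Interventions and Interactions): 9 − 7 = at least 2 days after quitting.
- At Visit 1 (Table 1 marks that column as the quit date): 9 − 0 = at least 9 days after quitting.

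A slower schedule, which the Design section also allows, only makes Visit 10 later. Under either date, successful quitters at Visit 10 are well beyond 6 hours without cigarettes.

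**Step 4: baseline.** If the Visit 1 reading is the baseline, r at Visit 1 is reading/itself = 1.00 for everyone. The written floor then passes every participant at that visit, and a corrected ceiling would fail every participant. Reversing the inequality therefore works only if the baseline comes from before the check first applies.

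**Step 5: does 50% correspond to 6 hours?** The documents give no elimination half-life. As an illustration only, assume first-order decline with no background level, so that r after t hours is 0.5^(t/h), with the half-life h between 2 and 8 hours.

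| h (hours, assumed) | r after 6 h | r after 24 h |
|---|---|---|
| 2 | 0.125 | 0.0002 |
| 3 | 0.250 | 0.0039 |
| 4 | 0.354 | 0.0156 |
| 5 | 0.435 | 0.0359 |
| 6 | 0.500 | 0.0625 |
| 8 | 0.595 | 0.125 |

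Across this range, someone abstinent for a day is at 0.125 or less and fails the written floor. At exactly 6 hours r runs from 0.125 to 0.595, so whether a 50% ceiling matches 6 hours depends on the half-life. That is why the sponsor should confirm the figure.

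**The case against.** The strongest reply is that the intent is plain. The sentence states its own purpose, the next two explain why deprivation is wanted, and the section adds that the team has used this procedure successfully and often. Trained staff are unlikely to admit people who have just smoked and refuse those who are deprived. On that view it is a one-phrase slip of little consequence. Much of this is fair: it makes literal application less likely. It does not correct the text, and citing past experience does not state the direction of the rule.

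Second, no bias is shown. The check is the same in both arms, participant and coordinator are blinded, and CO is recorded at Visits 1–10 and follow-ups, so smoking state can be recovered afterwards. This stands. It does not settle who is let through on the day.

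Third, that last worry assumes a failed reading has a consequence, and the protocol states none. Gatekeeping is inferred from the reading being required. This is also fair, so nothing is claimed here about missing data or exclusions.

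Fourth, a consent-visit baseline is a natural reading, because breath CO is taken at all visits and the consent visit is mentioned in the next sentence. That is possible. However, Table 2 lists CO only from Visit 1 and the consent visit is named only for cotinine, so the protocol leaves the point open.

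**Conclusion.** The contradiction holds. As written, the check gives the wrong verdict at every ratio to baseline except exactly 0.50, and nothing elsewhere in the protocol restates it as a reduction or an upper limit. The conclusion rests only on the protocol's own description of CO as a marker of recent smoking. It does not depend on the assumed half-lives or on which quit date is correct.

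The affected rule is mandatory and precedes the primary measures, so it should be fixed rather than left to interpretation. The practical effect is unquantified: it depends on how staff apply the sentence and on what follows a failed check. No effect on power, sample size or the treatment estimate is shown or claimed.

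**What to change.** Rewrite the criterion to match its purpose: a CO reading no more than 50% of baseline, that is, a fall of at least 50%. Ask the sponsor to confirm that 50% is consistent with 6 hours without cigarettes. In the same edit:

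- Name the baseline reading as one taken while the participant is smoking as usual and before the first visit at which the check applies. The protocol does not currently ask for this, but a 50% fall cannot be measured against a reading that is already deprived or is compared with itself.
- Have the sponsor state what follows a failed check.

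The cost is one changed phrase, two short statements and a check that the visit form carries the same direction. No extra procedures or participants are needed.
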